Subjects will be recruited from the COI's own practice. He may get some referrals from his colleagues that work in the same clinic such as [name], [name] and other collaborators. We have included a Waiver of Partial Consent to cover our screening process. The COI will identify eligible subjects and alert the coordinator. The coordinator will review all the details of the study with the subject and/or their family. If the subject agrees to participate in the study, they will be screened and then enrolled into the study.

This study will include patients who are age 18-85. We understand that subjects who are older age may be at a greater risk for cognitive impairments. However, if the PI feels that a subject may have diminished cognitive capacity, he will determine that the patient can not be enrolled in the study. Therefore, the research team will have this information available when they consent the patient. As there is a risk of loss of confidentiality, the PI and staff will take ample measures to code as much of the information as possible.

Please note that all subjects will be consented before any screening procedures are done.

Spanish speakers will be consented using a full Spanish version of the consent. We have Spanish speaking coordinators on staff that can receive consent from Spanish speaking patients.

Reconsent plan: Patients who were previously enrolled will be called and asked if they are willing to participate in the optional follow-up visit. If they agree, the consent form will be mailed and they will be asked to sign and mail it back or they will come in-person to be consented.

Are foreign language consent forms required for this protocol?

Yes

Which of the following ways will you document informed consent in languages other than English? A full-length informed consent document

J3. Privacy and Intrusiveness

Will the research involve observation or intrusion in situations where the subjects would normally have an expectation of privacy?

No

J4. Children

Will children be enrolled in the research?

No

J5. Neonates

Will non-viable neonates or neonates of uncertain viability be involved in research? No

J6. Consent Capacity - Adults who lack capacity

Will Adult subjects who lack the capacity to give informed consent be enrolled in the research? Yes

J7. Prisoners

Will Prisoners be enrolled in the research? No

Section K: Research Related Health Information and Confidentiality

Will research data include identifiable subject information?

Yes

- Information from health records such as diagnoses, progress notes, medications, lab or radiology findings, etc. Yes
- Specific information concerning alcohol abuse: Yes
- Specific information concerning drug abuse: Yes
- Specific information concerning sickle cell anemia: No
- Specific information concerning HIV: No
- Specific information concerning psychiatry notes: No
- Demographic information (name, D.O.B., age, gender, race, etc.): Yes

Full Social Security #: Yes

....

- Partial Social Security # (Last four digits): No
- Billing or financial records:

Yes

- Photographs, videotapes, and/or audiotapes of you: Yes
- Identifiable biospecimens

No

Other:

No

- At what institution will the physical research data be kept? The physical research will be kept in our BCM offices housed in the [name].
- How will such physical research data be secured?
 - Data will be kept in locked file cabinets that only the research team has access to.
- At what institution will the electronic research data be kept?
 - Electronic data will be kept on network computers in our BCM offices, under the password protected server. Address : \\discovery1.ad.bcm.edu\bcm-dept-icamp
 - Additional electronic data may be stored on REDCap. REDCap is hosted by Baylor College of Medicine Institute for Clinical & Translational Research.

The data from the eKare Insight camera is not stored on the camera itself, rather it is saved to the eKare cloud platform which research staff will be able to access via a web portal. This website is secure and follows all HIPAA, 21 CFR Part 11, Data Security and Protection Toolkit, and Cyber Essentials Certification requirements. Photos will not be able to be identified to patients and no PHI will be added.

Such electronic research data will be secured via BCM IT Services- provided secured network storage of electronic research data (Non-Portable devices only):

Yes

Such electronic research data will be secured via Other:

Yes, (describe below):

Electronic data will be stored using the REDCap (Research Electronic Data Capture) software. This software is used to electronically collect and manage research data. REDCap is a secure, web-based platform.

Electronic data will also be stored and secured under the password protected server provided by BCM IT Services.

Will there be anyone besides the PI, the study staff, the IRB and the sponsor, who will have access to identifiable research data?

No

Please describe the methods of transmission of any research data (including PHI, sensitive, and non-sensitive data) to sponsors and/or collaborators.

Transmissions, if any, will only happen via secure emails.

Will you obtain a Certificate of Confidentiality for this study? No

Please further discuss any potential confidentiality issues related to this study. NA

Section L: Cost/Payment

Delineate clinical procedures from research procedures. Will subject's insurance (or subject) be responsible for research related costs? If so state for which items subject's insurance (or subject) will be responsible (surgery, device, drugs, etc). If appropriate, discuss the availability of financial counseling.

Participating in this study will take the subject's time and will not involve any direct cost to him/her. The subject's medical insurance will be billed for all standard of care related expenses including:

Wound care (CPT 97597), Post-op visit (99024) on visits 0, 2, and 4, Hba1c (CPT 83036) at visit 0 only if not previously available on EPIC

If subjects will be paid (money, gift certificates, coupons, etc.) to participate in this research project, please note the total dollar amount (or dollar value amount) and distribution plan (one payment, pro-rated payment, paid upon completion, etc) of the payment.

Dollar Amount:

450

Distribution Plan:

Subjects will be compensated \$75 per in-person visit. We will be also providing parking validations. If a patient attends a remote visit, compensation will be \$25.

Subjects will be given a ClinCard where payments will be loaded after a study visit is completed. Additional information will be provided to the subject about how to manage the card.

We will be requesting subjects SSN for payment purposes. This is required in order to provide them with a ClinCard.

Section M: Genetics

How would you classify your genetic study?

Discuss the potential for psychological, social, and/or physical harm subsequent to participation in this research. Please discuss, considering the following areas: risks to privacy, confidentiality, insurability, employability, immigration status, paternity status, educational opportunities, or social stigma.

Will subjects be offered any type of genetic education or counseling, and if so, who will provide the education or counseling and under what conditions will it be provided? If there is the possibility that a family's pedigree will be presented or published, please describe how you will protect family member's confidentiality?

Section N: Sample Collection

None

Section O: Drug Studies

Does the research involve the use of ANY drug* or biologic? (*A drug is defined as any substance that is used to elicit a pharmacologic or physiologic response whether it is for treatment or diagnostic purposes) No

Does the research involve the use of ANY gene transfer agent for human gene transfer research? No

O1. Current Drugs

Is this study placebo-controlled? No

Will the research involve a radioactive drug? No

Section P: Device Studies

Does this research study involve the use of ANY device? Yes

Device 1: Transcu O2 device

Device 2: Sensilase

Device 3: Zephyr Bioharness

Device 4: Legsys

Device 5: Kent camera

Device 6: Silagen Silicone Sheet

Device 7: inSight

Section Q: Consent Form(s)

EVALUATION OF OXYGEN DELIVERY WITH TRANSCU O2 TO STUDY SUCCESS RATE OF SURGICALLY CLOSED WOUNDS - A RANDOMIZED CONTROLLED TRIAL.

Section R: Advertisements

None

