Section D: Purpose and Objectives

This is an exploratory randomized controlled trial study to test feasibility, acceptability, and proof of concept efficacy of Continuous Diffusion of Oxygen (CDO) adjunct therapy for decreasing healing time and reducing tissue dehiscence post breast reconstruction. We will assess the benefit of this novel adjunct therapy on successful closure, tissue oxygenation, scar appearance, and patients centered outcomes including perception of benefit, pain, sleep quality, and quality of life. Since all procedures are bilateral, an internal randomization will be performed based on breast side (left or right). The patients will be given CDO in one breast defined as intervention breast. A 5x5 cm CDO dressing will be placed by the plastic surgeon over the T-inframammary fold after the Dermabond glue and Prineo tape are placed. Then, Silagen (a silicon sheet) will be placed on top of the CDO dressing to secure it in place. The remaining parts of the incision will be covered with Dermabond Glue and Prineo tape. On the contrary, the control breast will be given the standard dressing (Dermabond + Prineo tape). The study device OxyGeni is a Class II medical device which has US Food and Drug Administration (FDA) 510(k) clearance, CE-Mark approval and a Health Canada license for the treatment of wounds.

Outcomes will be assessed on weekly-basis up to 4 weeks. Here are the aims and hypotheses for this study:

Aim1: To assess effectiveness of CDO adjunct therapy in reducing the likelihood of wound complication post-surgical

closure.

H1: CDO adjunct therapy will reduce the likelihood of surgical wound complication including dehiscence and its volume, infection or surgical revision, compare to standard of care dressing.

Aim2: To assess changes in skin perfusion in patients treated with CDO adjunct therapy.

H2: CDO adjunct therapy will improve tissue oxygen saturation in >50% of the patients as compared to baseline (measurements at baseline, 2 weeks, and 4 weeks).

Aim3: To evaluate changes in quality of life, anxiety during dressing change, and psychosocial parameters in patients with a surgical wound treated by CDO adjunct therapy

H3: CDO adjunct therapy will improve subject quality of life, reduce anxiety, and reduce perceived pain and physiological stress response during dressing change compared to the control group.

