Please note that subjects will be consented before performing any study related measurements. This study will not bring any direct costs to the subject. The subject's medical insurance will be billed for all standard of care procedures.

Eligible subjects will be internally randomized and will receive the intervention for 4 weeks. Each subjects will receive standard of care for wound treatment. Intervention side will receive adjunct Continuous Diffusion of Oxygen (CDO) therapy using a novel dressing, which facilitates continuous supply of oxygen to the wound inside the wound dressing using a portable device named OxyGeni . We will collect patient demographics (e.g., age, sex, height, weight, race, ethnicity, marital status, level of education, etc), relevant medical history (e.g., comorbidity, type of surgery, number of prescription and over counter medication, etc), and relevant social factors (e.g., marital status, years of education, type of work, tobacco history, etc) at baseline. Primary outcomes include tissue oxygenation (assessed using Kent Imaging system) and incidence of wound complications (e.g. dehiscence, infection, and surgical revision). Primary outcomes will be assessed at baseline and on a weekly basis for up to 4 weeks. Secondary and exploratory outcomes include inflammation (assessed using a KENT camera), pain (assessed visual analog scale). The secondary and exploratory outcomes will be assessed at baseline and week-4. Other optional assessments include quality of life (NIH Global Health PROMIS), depression (Center for Epidemiologic Studies Depression Scale, CES-D), cognitive function MoCA), and psychosocial metrics (e.g. fatigue, anxiety, frailty, sleep, etc). These assessments are optional and will be done upon time availability and patient acceptance. We anticipate that duration of all assessments will not exceed 60 minutes. We will be reviewing the billing records for our

patients to explore costs of both groups. We may visit the patient's home for an appointment that doesn't require the physician present or to fix any issues with the device.

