Visit 5, at minimum 6 months post-op *duration: 50 minutes. This is an optional visit where research staff will take a NIRS image, a Digital Photograph, report adverse events since last visit, and assess patient scar satisfaction using validated questionnaires (PASS and POSAS). Moreover, the plastic surgeon will provide their observation of the scarring using validated questionnaires (SCAR and POSAS). The patient will be seen in the Vascular Clinic (Procedure Room). Female research coordinator will perform all measurements and questionnaires under ethics protocol. Should the patient not be available to attend the clinic in-person, they will have the option to do the questionnaires remotely and upload digital photos of the area via RedCAP. This study visit is added to provide long-term information regarding scarring and effect of study device on long-term healing outcomes.

The research coordinator will make sure at all times that patient does not experience discomfort and all ethical protocols will be followed.

Section G: Sample Size/Data Analysis

G1. Sample Size

How many subjects (or specimens, or charts) will be used in this study? Local: 30 Worldwide: 30

Please indicate why you chose the sample size proposed:

This is an exploratory proof of concept study. The anticipated sample size (n=30) is selected based on resource/budget availability and feasibility to be completed within one year. This sample size is estimated to be sufficient to determine feasibility and proof of concept efficacy of Continuous Diffusion of Oxygen (CDO) adjunct therapy to improve tissue oxygen supply and reduce likelihood of adverse events. Upon initial results and availability of budget, the sample size may be increased to clinically validate the initial observation. In this case, an addendum will be submitted to increase sample size if needed.

G2. Data Analysis

Provide a description of your plan for data analysis. State the types of comparisons you plan (e.g. comparison of means, comparison of proportions, regressions, analysis of variance). Which is the PRIMARY comparison/analysis? How will the analyses proposed relate to the primary purposes of your study?

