The primary outcomes of this study are 1) tissue oxygen saturation level measured using Kent Imaging system and 2) incident of wound related adverse events (e.g., incident wound dehiscence, infection, scar size, and surgical revision). Secondarily outcomes include pain, wound outcomes (e.g. wound size, scar size, wound healing rate, etc assessed using digital photography), area of inflammation (assessed using KENT), and pain (assessed using VAS). Exploratory outcomes include patient quality of life, sleep quality, anxiety, and depression. Baseline between group comparison will be dine using two-sample t-tests, Mann-Whitney U-test, or Chi-square depend on scale/distribution of the variables (i.e., parametric, non-parametric, or binary). We will use general mixed linear model and post-hoc analysis to examine difference between

groups (time, group, and time X group effect) for skin perfusion. We will adjust the results based on baseline incision wound size and duration between baseline and last visit assessment. Subjects with at least one week continue treatment will be included in the analysis. Controlled variables include age, BMI, baseline vascular health. We will use chi-square to estimate whether the number of wound complication incidents is less in the intervention group compared to the control group. Chi-square or repeated ANOVA or Mann-U test depend on scale/distribution of the variable will be used for secondary and exploratory outcomes.

Section H: Potential Risks/Discomforts

H1. Potential Risks/Discomforts

Describe and assess any potential risks/discomforts; (physical, psychological, social, legal, or other) and assess the likelihood and seriousness of such risks:

As any new investigational device, there are some risks, which are anticipated to be minimal in this study. Some of potential risks could be: * Skin related discomfort, erythema (redness), skin rash, dryness and itching. * Skin allergic reaction to dressing adhesive. * Tenderness/minor ache around the dressing application area * Heat sensation and/or perspiration with wearing dressing * Some impairment of mobility due to dressing unit

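### CDO is randomised by breast side, but left/right balance is unspecified and the G2 perfusion model has no side term: a minor, cheap gain in precision is left unused

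*Combined protocol and SAP*

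**What the plan says.** Section D, and again the baseline paragraph of F1, sets the unit of randomisation: "Since all procedures are bilateral, an internal randomization will be performed based on breast side (left or right"). Each patient therefore supplies one treated breast and one control breast. Neither place gives a ratio, a list, blocking or a target number of left and right allocations, although the form's prompt in F1 asks about the chance of assignment to each group.

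G1 fixes the size: "The anticipated sample size (n=30) is selected based on resource/budget availability and feasibility to be completed within one year". F2 names the endpoints: "Primary outcomes include tissue oxygenation (assessed using Kent Imaging system) and incidence of wound complications (e.g. dehiscence, infection, and surgical revision").

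G2 plans a mixed linear model for differences between "groups (time, group, and time X group effect) for skin perfusion". It adds: "We will adjust the results based on baseline incision wound size and duration between baseline and last visit assessment", and "Controlled variables include age, BMI, baseline vascular health". For the other primary outcome: "We will use chi-square to estimate whether the number of wound complication incidents is less in the intervention group compared to the control group". Breast side appears in neither analysis. G2 also does not say that a patient's two breasts are analysed as a pair.

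**The concern.** In a within-patient trial on two sides, left versus right plays the part that period plays in a crossover. It is known without error for every breast, and it is the factor that was randomised. Any systematic difference between sides that is not modelled goes into the error of the CDO-minus-control difference.

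The covariates that G2 does list mostly cannot help with this. Age, BMI and vascular health, and normally length of follow-up, are the same for both breasts of a patient, so they cannot explain a within-patient difference. Side can.

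What is at stake is some precision in a trial whose 30 patients are set by resources, so lost precision is not easily recovered by recruiting more.

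**Working it through.** **No figure to reproduce.** The documents give no SD, effect size, alpha, power or left-right difference. Everything below except the number of patients is an assumption.

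**Inputs.** 30 patients, hence 30 pairs (G1). One CDO and one control breast per patient (Section D). Left-right difference δ, in units of the SD of the paired difference: assumed 0.1, 0.3 and 0.5.

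**Model.** For patient i, the CDO-minus-control difference is d = τ + sδ + e, where s = +1 if CDO is on the left and −1 if on the right, and SD(e) = 1.

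**1. Cost of omitting side, simple randomisation.** The variance of d is 1 + δ², so the standard error is multiplied by √(1 + δ²). The last column shows what happens to an illustrative 80% power.

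| δ | √(1 + δ²) | Rise in SE | 80% power becomes |
|---|---|---|---|
| 0.1 | √1.01 = 1.005 | 0.5% | 79.6% |
| 0.3 | √1.09 = 1.044 | 4% | 76.5% |
| 0.5 | √1.25 = 1.118 | 12% | 70.7% |

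At δ = 0.5, 30 patients give the precision of 30/1.25 = 24.

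**2. Chance shift, simple randomisation.** With nL patients given CDO on the left and nR on the right, the estimate moves by δ(nL − nR)/30. Its mean is 0 and its SD is δ/√30 = 0.18δ. From Binomial(30, 0.5):

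- 18:12 or worse: probability 0.36, shift at least 6/30 = 0.20δ.
- 20:10 or worse: probability 0.099, shift at least 10/30 = 0.33δ (0.17 SD at δ = 0.5).

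**3. Behaviour of the test.** Simulated with 20,000 runs per setting, two-sided 5% level and a true effect of 0.53 SD for power:

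| δ | Allocation | Side in model | Type I error | Power |
|---|---|---|---|---|
| 0 | simple | no | 0.051 | 0.805 |
| 0 | simple | yes | 0.052 | 0.790 |
| 0 | 15:15 | no | 0.050 | 0.804 |
| 0 | 15:15 | yes | 0.051 | 0.798 |
| 0.3 | simple | no | 0.047 | 0.763 |
| 0.3 | simple | yes | 0.049 | 0.787 |
| 0.3 | 15:15 | no | 0.040 | 0.775 |
| 0.3 | 15:15 | yes | 0.050 | 0.801 |
| 0.5 | simple | no | 0.051 | 0.711 |
| 0.5 | simple | yes | 0.049 | 0.781 |
| 0.5 | 15:15 | no | 0.028 | 0.731 |
| 0.5 | 15:15 | yes | 0.047 | 0.803 |

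Under simple randomisation the error rate holds and power is lost. Under a balanced list the shift is zero, but without the side term the test is conservative. The side term restores power to about 0.78 to 0.80 either way, so balancing alone is not enough.

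**4. Which contrast is affected.** Suppose baseline oxygenation is measured in each breast and the left-right offset is constant. The change from baseline then removes the offset, and the time x group estimate is untouched. With complete data, a side main effect does not change that estimate either. What remains exposed is the group main effect, any side difference that changes over time (which needs side x time), and per-breast outcomes with no baseline, such as scar scores and complications.

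**The case against.** The strongest case against has four parts.

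- **Silence is not imbalance.** A reader might infer that allocation is unbalanced by side. The documents do not support that: the wording in Section D and F1 fits a 15:15 blocked list as well as simple randomisation. The supportable statement is that the method is unspecified. This part stands, and step 2 of the working is conditional on it.
- **Baseline removes much of the problem for oxygenation.** A reader might infer that any left-right difference contaminates the oxygenation result. H2 in Section D concerns improvement from baseline, and G2 plans a baseline comparison between groups, which suggests a baseline image of each breast. If so, a fixed offset cancels from time x group. This stands in part. The baseline-visit text in F2 does not say that both breasts are imaged, G2 also tests the group main effect, and a side difference present at closure but gone by the weekly visits would not cancel.
- **It is not bias.** A reader might infer that left-right imbalance could pass for a treatment effect more often than the nominal error rate allows. It does not: the shift averages zero and simulated type I error under simple randomisation stays near 5%. This part stands in full.
- **The size is unknown.** No section mentions operating order, systematic asymmetry or side-specific imaging. Asymmetry whose direction varies between patients is not a side effect and would not be removed by a side term. At 0.3 SD or less the standard error rises by about 4% at most. This stands, and it limits the severity.

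Pairing also comes first. The precision figures presume a paired analysis, which G2 does not state. That gap is probably larger than this one.

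**Conclusion.** The omission is real: side is what was randomised, its balance is unspecified, and neither primary analysis includes it. The consequence is modest. If a systematic left-right difference exists, leaving side out costs about 0.5% to 12% in standard error over an assumed 0.1 to 0.5 SD, or makes the test conservative if the list is in fact balanced (type I error about 0.028 at 0.5 SD).

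The documents do not support a finding of actual imbalance, of systematic bias, or of an inflated false-positive rate. The point applies to the group main effect, to side differences that change over time, and to per-breast outcomes without a baseline. It rests on the two breasts being analysed as a pair. In an exploratory pilot this is a minor, cheap improvement.

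**What to change.** 1. State the allocation method. If the list has not already been used, generate it in permuted blocks that give 15 CDO-left and 15 CDO-right.
2. In the G2 mixed model, include patient as the random (pairing) factor, and add side and side x time as fixed effects.
3. Add side as a fixed effect to the continuous per-breast secondary models, for example scar scores.
4. State that baseline oxygenation is measured in each breast, if that is the intention.

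No side term is proposed for complications. At the 10% to 15% rate in Section C, applied per breast, the control side would have about 30 × 0.10 = 3 to 30 × 0.15 = 4.5 events. For that outcome the benefit comes from the balanced list.

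**Cost.** One degree of freedom for side. Baseline and weeks 1 to 4 give five time points, so side x time takes 5 − 1 = 4 more. If there is no left-right difference the loss is negligible: simulated power for the side term alone goes from 0.804 to 0.798 under a 15:15 list, and from 0.805 to 0.790 under simple randomisation. No new data are needed, and if allocation is already complete the model terms still work on their own.
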